### **Exclusion Criteria**

1. HIV positive patients.
2. Patients who are recipients of multiple solid organ or islet cell tissue transplants, or have previously received an organ or tissue transplant.
3. Patients with renal failure or CKD/ESRD who require renal replacement therapy for more than 2 weeks prior to transplantation.
4. History of malignancy of any organ system within the past 5 years whether or not there is evidence of local recurrence or metastases, other than non-metastatic basal or squamous cell carcinoma of the skin or HCC (see next criteria).
5. HCC that does not fulfill Milan criteria (1 nodule  $\leq$  5 cm, 2-3 nodules all  $\leq$  3 cm) at the time of transplantation.
6. Patients with a known hypersensitivity to the drugs used on study or their class, or to any of the excipients.
7. Patients receiving drugs known to significantly interact with any immunosuppressant used in the trial.
8. Patients who are recipients of AB0 incompatible transplant grafts.
9. Patients with a current systemic infection or sepsis requiring active use of IV antibiotics.
10. Patients with symptoms of significant mental illness and with inability to cooperate or communicate with the investigator. Patients who are unlikely to comply with the study requirements, or who are unable to give informed consent.
11. Women
  - o who are pregnant or breast feeding (pregnancy defined as the state of a female after conception and until the termination of gestation, confirmed by a positive hCG laboratory test ( $> 5$  mIU/ml)).

- who are menstruating and capable of becoming pregnant\* and not practicing a medically approved method of contraception (Pearl Index <1\*\*) during and up to at least 4-8 weeks after the end of treatment. A negative pregnancy test (serum) for all women entering menarche is required with sufficient lead time before inclusion.  
\*definition of post-menopausal: 12 months of natural (spontaneous) amenorrhea or 6 months of spontaneous amenorrhea with serum FSH levels >40 mIU/m or 6 weeks post surgical bilateral oophorectomy with or without hysterectomy  
\*\*examples of particularly reliable methods with Pearl Index (PI) <1, according to guidelines of Deutsche Gesellschaft für Gynäkologie und Geburtshilfe:
  - Combination pill with estrogen and gestagen (no mini-pill, PI=0.1-0.9)
  - Vaginal ring (NuvaRing®, PI=0.65 uncorr.; 0.4 corr.)
  - Contraceptive patch (EVRA®, PI= 0.72 uncorr.; 0.9 corr.)
  - Estrogen-free ovulation inhibitors (Cerazette®, PI=0.14)
  - Progestin-containing contraceptives (Implanon®, PI=0-0.08)
  - Injectable 3-month depot progestins (PI=0.3-1.4; 0.88 corr.)
  - Intra-uterine progestine device (Mirena®, PI=0.16)
- Highly effective contraception methods include total abstinence (when this is in line with the preferred and usual lifestyle of the subject). Periodic abstinence (e.g. calendar, ovulation, symptothermal, post-ovulation methods) and withdrawal are not acceptable methods of contraception.

12. Patients, who have already been randomized into this study earlier must not be included a second time.

13. Participation in another clinical trial.

#### **Inclusion Criteria - Randomization**

1. eGFR (MDRD4 formula) > 30 mL/min/1.73m^2 at time of randomization.
2. Absence of thrombosis via Doppler ultrasound of the major hepatic arteries, major hepatic veins, portal vein and inferior vena cava at time of randomization and prior to any initiation of treatment with everolimus.
3. Allograft is functioning at an acceptable level by the time of randomization as defined by total bilirubin levels  $\leq$ 3 times ULN and AlkP, AST, ALT levels  $\leq$  5 times ULN.

#### **Exclusion Criteria - Randomization**

1. Patients who are not able to take oral medication at time of randomization.
2. Patients with platelet count <50,000/mm^3)
3. Patients with an absolute neutrophil count of <1,000/mm^3
4. Patients with a white blood cell count of <2,000/mm^3)
5. Patients with hemoglobin < 6.0 g/dL.(transfusion of erythrocytes concentrate during or after transplantation are allowed according to investigator discretion.)
6. Patients with uncontrolled hypercholesterolemia (>350mg/dL; >9mmol/L) or hypertriglyceridemia (>750 mg/dL, >8.5 mmol/L).
7. Patients with a protein/creatinine ratio indicating daily urinary protein excretion >1 g/24h at time of randomization.
8. Patients with clinically significant or uncontrolled systemic infection requiring active use of IV antibiotics at the time of randomization.

9. Patients who have received an investigational drug within 30 days prior to randomization.

# **6 Treatment**

## **6.1 Patient numbering**

Each patient is uniquely identified in the study by a combination of his/her center number and patient number. The center number is assigned by Novartis to the investigative site. Upon signing the informed consent form, the patient is assigned a patient number by the investigator. At each site the first patient is assigned patient number 1, and subsequent patients are assigned consecutive numbers (e.g., the second patient is assigned patient number 2, the third patient is assigned patient number 3). Once assigned to a patient, a patient number will not be reused. If the patient fails to be randomized for any reason, the reason for not being randomized will be entered on the Screening Failure Log.

## 6.2 Investigational and control drugs

### Investigational drug

#### **Certican®**

Active ingredient: everolimus (RAD001)  
Galenic form: tablets  
Dose: one tablet containing 0.25mg, 0.5mg, 0.75mg or 1.0mg  
Dosing schedule: twice daily, dose according to blood levels  
Packaging: blisters of 10 tablets

### Other immunosuppressive drugs

- **Tacrolimus**

#### **Tacrolimus Hexal®**

Active ingredient: tacrolimus  
Galenic form: capsules  
Dose: one capsule containing 0.5, 1.0, or 5.0mg  
Dosing schedule: twice daily, dose according to blood levels  
Packaging: blisters of 10 capsules

- **Corticosteroids**

are mandatory within the first six months after TX.

Further immunosuppressive agents are excluded. Everolimus and Tacrolimus Hexal® will be supplied by Novartis.

## 6.3 Treatment arms

At Baseline (Visit 2) between 7 and 21 days post LTx patients will be assigned to one of the following two treatment groups in a ratio of 1:1.

- **EVR/TAC group (ARM I):**

Everolimus (C0-h: 3-8 ng/mL\*) + tacrolimus (C0-h: < 5 ng/mL\*)

- **TAC group (ARM II):**

Tacrolimus (C0-h: 6-10 ng/ml\*)

\*Trough levels as per local practice, e.g. liquid chromatography coupled with mass spectrometry (LCMS). Values derived from enzyme based assays will be corrected (as described in the manufacturer's instructions).

## 6.4 Treatment assignment

At Baseline (Visit 2), which has to take place prior to randomization, all patients who meet the inclusion and do not fulfill any of the exclusion criteria will be given the lowest available number on the randomization list of the respective stratum. This number assigns them to one of the treatment arms. The investigator will enter the randomization number on the CRF.

The randomization numbers will be generated using the following procedure to insure that treatment assignment is unbiased and concealed from patients and investigator staff. A

randomization list will be produced under the responsibility of the Novartis Nürnberg GCP Officer using a validated system that automates the random assignment of treatment arms to randomization numbers in the specified ratio. Randomization will be stratified by HCV status (positive/negative) and lab MELD (Model of End Stage Liver Disease) score below/equal or above 30 at transplantation.

Randomization of individual patients will be performed centrally by a CRO. Allocation of a patient to one of the two treatment groups will be performed in the following steps.

1. Information about patient enrolment (Screening Visit):

Study sites will inform the CRO about each patient inclusion via fax

2. Randomization (Baseline Visit):

At day of randomization, the site will provide the information of eligible patient to the CRO by fax.

The CRO will allocate the patient the next free consecutive randomization number allocated to the site. Randomization number and allocated treatment (according to the randomization list) will be provided to the site by fax.

The randomization number will be entered on the CRF of an individual patient.

## **6.5 Treatment blinding**

Not applicable, since this is an open-label study.

## **6.6 Treating the patient**

### **6.6.1 Dispensing the study drug**

Each study site will be supplied by Novartis with Certican® and Tacrolimus Hexal®. Certican® will be provided as tablets in 0.25 mg, 0.5 mg, 0.75 mg and 1.0 mg strength, packaged in packages, and labeled according to the German legal requirements. Tacrolimus Hexal® will be provided as capsules in 0.5 mg, 1.0 mg and 5 mg strength.

Immediately before dispensing study drug (Certican®) to the patient, investigator staff will detach the outer part of the label from the packaging and affix it to the source document (Drug Accounting Form) containing that patient's unique patient number. Tacrolimus Hexal® dispensing will be also recorded on the Drug Accounting Form.

### **6.6.2 Instructions for use of study drug**

The starting dose will be 1 tablet of 1.0 mg everolimus in the morning, and 1 tablet of 1.0 mg in the evening for all patients. First dose of study drug has to be applied within 24h after randomization.

Additional medication for dose adjustments will be provided in 0.25 mg, 0.5 mg and 0.75 mg tablet strengths. The dose will be adjusted to maintain the everolimus trough blood levels between 3-8 ng/mL. Five (5) days after randomization or any later, everolimus dose should be doubled if the trough level is below 3 ng/mL. The trough level should not exceed 8 ng/mL during the whole study duration.

Target level of Certican® should be achieved within 14 days post randomization. Close monitoring of trough levels is required at least once monthly.

Patients in Arm 1 will take everolimus (C0-h: 3-8 ng/mL) twice daily in 12 hours intervals simultaneously with tacrolimus (C0-h: < 5 ng/mL), on a consistent schedule with regards to time of day and relation to meals. No grapefruit or grapefruit juice should be taken at all throughout the study.

The investigator should promote compliance by instructing the patient to take the study drug exactly as prescribed and by stating that compliance is necessary for the patient's safety and the validity of the study. The patient should be instructed to contact the investigator if he/she is unable for any reason to take the study drug as prescribed.

At each patient's study visit, site personnel should count remaining study medication (everolimus, tacrolimus) to check compliance.

All dosages dispensed to and returned by the patient during the study must be recorded on the Drug Accounting Form in the Investigator Folder. Patients randomized to a specific immunosuppressive regimen in Arm I or Arm II have to remain on this medication up to the end of the study – otherwise the patient will be discontinued from the study drug regimen.

Patients may be seen by local general practitioner in between protocol defined visits. The main PI is responsible to give guidance to the local general practitioners for patient's management. The PI is responsible to obtain all information about measured levels of immunosuppressive medications and changes of dosages throughout the study.

### **6.6.3 Permitted study drug dose adjustments and interruptions**

For patients who are unable to tolerate the protocol-specified dosing scheme, dose adjustments and interruptions are permitted in order to keep the patient on study drug. All changes must be recorded on the Dosage Administration Record CRF.

The following guidelines should be followed as far as clinically feasible:

#### **Everolimus**

Because everolimus is the mainstay of the protocol in the investigational arm (Arm 1), everolimus dose should be continued on a stable level according to trough levels. Treatment interruptions and dose reduction will be allowed for those patients who do not tolerate the prescribed dose of everolimus indicated by the occurrence of adverse events.

In both renal and heart transplantation, everolimus trough concentrations  $\leq$  3 ng/mL were associated with a significantly lower protection from acute rejection compared with trough levels  $>$  3 ng/mL. Although hyperlipidemia was common over the full exposure range, it responded to corticosteroid dose reduction, dietary management, and lipid-lowering therapies, and were, therefore, not dose-limiting. The incidence of leukocytopenia did not show any exposure-response relationship to everolimus trough concentrations. The incidence of notable thrombocytopenia ( $<$  100x10^9/L) increased with everolimus exposure; however, the incidence of clinically meaningful platelet reductions ( $<$  75x10^9/L) was generally low.

In severe hematologic adverse events (CTCAE 4.0) including leukocytopenia and thrombocytopenia everolimus should be interrupted until the condition has resolved. If a hemolytic uremic syndrome (hemolytic anemia, acute renal failure, uremia) occurs, everolimus has also to be permanently discontinued.

In case of a decrease of renal function all potential nephrotoxic medication other than the immunosuppressive agents should be discontinued first. If stadium 1 of acute kidney injury is met (an increase in SCr  $\geq 0.3$  mg/dL or  $25\mu\text{mol}/\text{L}$  (Chertow, 2005) or an increase in SCr of 50-100% from the initial value (Mehta, 2007)), everolimus and tacrolimus has to be reduced to the lowest trough levels according to the protocol (see above). If the acute kidney injury is not responsive to these measures, everolimus has to be discontinued.

Target therapeutic ranges for everolimus whole blood trough levels should be 3-8 ng/mL.

Dose should be adjusted if everolimus whole blood trough levels outside the target range are measured. Dose adjustments of everolimus should be monitored  $5 \pm 2$  days later by a measurement of the everolimus blood trough level.

For patients who are unable to tolerate the protocol-specified dosing scheme due to a decrease in the platelet count, a decrease in hemoglobin level, a decrease in white blood cell count, an increase in cholesterol level, an increase in triglyceride level, or other adverse events, dose adjustments are permitted in order to keep the patient on investigational drug. The respective guidelines are appended to the clinical trial protocol (see Appendix 5).

The everolimus dose should be decreased by one dosing step (0.25mg b.i.d.) if a dose reduction is necessary. If a temporary reduction in everolimus level is needed the everolimus trough blood level should still be maintained no lower than 3 ng/mL. Everolimus should be discontinued if a trough level  $\geq 3$  ng/mL cannot be maintained due to toxicity. Severe and unremitting changes may also lead to investigational drug discontinuation.

If everolimus is interrupted for longer than 4 consecutive weeks, or more than 8 cumulative weeks, discontinuation of study medication should be discussed with the sponsor. Study drug may be interrupted during antibody treatment of rejection episodes. During the course of the trial the study drugs will be administered on a b.i.d. regimen. Study medication will not be provided to patients after they have discontinued the study.

If reduction of everolimus is necessary for the patient to remain in target trough range, everolimus dosing may be reduced by 0.25 mg intervals.

Appropriate information needs to be recorded on the Dosage Administration CRF.

The End of Treatment Visit will be performed and documented for all patients who are withdrawn prematurely from the treatment at time point of discontinuation. The Month 12 assessments will be performed for all patients randomized in the study.

### **Tacrolimus**

Dose should be adjusted if tacrolimus whole blood levels are outside the target range. Target therapeutic ranges for tacrolimus whole blood trough levels should be  $< 5$  ng/mL in the investigational arm (Arm I) and 6-10 ng/ml in the control arm (Arm II). In case of severe tacrolimus toxicity, dose reductions below the target levels may be performed on the investigators' discretion.

If tacrolimus medication is interrupted for more than 4 consecutive weeks, or more than 8 cumulative weeks, discontinuation of the tacrolimus should be considered.

### **Prednisone/Prednisolone**

Oral corticosteroids (prednisolone or equivalent) will be administered according to local practice during the trial. However, after randomization, the minimum dosage of corticosteroids must be equivalent to 5 mg prednisone/day. Corticosteroids may not be discontinued earlier than Month 6 post-transplantation.

#### **6.6.4      Rescue medication**

##### **Treatment for acute rejection episodes**

Treatment for biopsy proven acute rejection will commence at the clinician's discretion or according to the center-specific protocol. An acute rejection episode will be considered to have been treated if a patient has received at least 3 days' treatment with a daily dose of 15mg/kg (max.1000 mg) or more of i.v. methylprednisolone (or equivalent) and/or at least 3 days of antilymphocyte therapy.

Treatment of acute rejection or presumed acute rejection will be recorded on the appropriate CRF page.

The biopsies will be read locally and the severity of acute rejection will be classified using the Rejection Activity Index (RAI) as defined by the World Gastroenterology Consensus Document (Banff, Hepatology 1997). In the event that a rejection episode is not confirmed by biopsy or a biopsy is not done, the clinician will score the severity of that rejection episode on the basis of clinical and functional criteria into severe (hospitalization, death) and non severe (all others).

#### **6.6.5      Other concomitant treatment**

##### **Cytomegalovirus prophylaxis**

Cytomegalovirus (CMV) prophylaxis or preemptive monitoring for CMV should be according to local practice and applied uniformly for all enrolled patients at the center. Treatment with valganciclovir, ganciclovir, cytomegalovirus hyperimmune globulin, acyclovir or valacyclovir is permitted and will be administered according to local practice. CMV prophylaxis is also recommended for CMV Donor positive, Recipient negative (D+/R-) patients and following any antibody treatment of acute rejection episodes.

##### ***Pneumocystis carinii* pneumonia prophylaxis**

Prophylactic treatment for pneumocystis carinii pneumonia (PCP) consisting Bactrim® or equivalent (trimethoprim / sulfamethoxazole), starting when oral medication can be tolerated will be used as per local practice. Aerolized pentamidine (300 mg/month) or dapsone (100 mg/day) should be administered to patients unable to tolerate trimethoprim / sulfamethoxazole as per local practice.

##### **Treatment of oral Candida**

All patients will be treated according to local standard of care. The same prophylaxis strategy should be applied for all patients at a given site. Nystatin suspension in a swish and swallow regimen is recommended for the prophylaxis or treatment of oral thrush (Candida). Alternative clotrimazole lozenges/troches may be used. Routine use of systemic antifungal "azole" agents (i.e. ketoconazole, itraconazole, voriconazole and fluconazole) for oral candidiasis will not be allowed unless patients are systemically infected. Administration of

“azoles” may increase blood concentrations of both tacrolimus and everolimus; therefore their use should be minimized. Particular attention to side effects is required (see [Appendix 3](#)).

### **Hepatitis B prophylaxis**

Prophylaxis for recurrent hepatitis B during the course of this study will be left to the investigator’s discretion.

### **Treatment of HCV disease**

Treatment for HCV disease can be done but not preemptively. Investigators will be allowed to treat HCV only when recurrent HCV disease has been documented, based on histological evidence as determined by the local pathologist. Therapies used for post-transplantation HCV disease will be documented on the appropriate CRF section. HCV patients should not receive HCV therapy during the time of tacrolimus elimination.

### **Recommended follow-up for HCC patients**

It is highly recommended to monitor and follow-up the HCC patients as per the best local practices. Patients may be evaluated every three months during the 12 months study duration. In addition to the routine laboratory monitoring/tests, tumor markers (AFP-alphaprotein) and hepatic ultrasound may be performed on a quarterly basis and computed tomography scans (CAT, CT) or MRI (especially Fe-MRI) twice a year.

### **Other medication**

The investigator should instruct the patient to notify the study site about any new medications he/she takes after the start of the investigational drug. All medications (other than investigational drug) and significant non-drug therapies (including physical therapy and blood transfusions) administered after patients screening visit must be listed on the Prior-/Concomitant Medications/Significant Non-Drug Therapies pages in the CRF. If administered for an AE, it should be appropriately cross-referenced on the AE CRF.

#### **6.6.6 Study drug discontinuation**

In case of elevated cholesterol and/or triglyceride levels, lipid lowering medications should be optimized. HMG Co-A reductase inhibitors (e.g., fluvastatin) are to be administered according to local practice for the management of hyperlipidemia. The use of lovastatin is prohibited in this study. The starting dose of HMG Co-A reductase inhibitors will be equivalent to 20 mg pravastatin, 5 mg simvastatin or 20 mg fluvastatin, and may be increased to target and maintain a LDL level of < 130 mg/dL. Lipid lowering therapy should be optimized before dosage reduction of study medication is considered. If the elevation persists, the dosing of everolimus should be adjusted following the recommendations given in [Appendix 5](#).

Dose may be reduced for those patients with other moderate/severe AEs according to the investigators’ judgment. Also in these cases, the medication doses can be reduced by half or interrupted until event resolves.

If the everolimus medication is interrupted for more than 4 consecutive weeks, or more than 8 cumulative weeks within the 12 months study treatment, discontinuation of the respective medication should be considered and the patient withdrawn from study treatment.

Patients who discontinue study drug before completing the 12-months period should be scheduled for a visit as soon as possible, at which time all of the assessments listed for the final visit (EoT, Visit 9a) will be performed. The End of Study Assessment (Visit 9, Month 12) should be repeated at the originally planned time point, i.e. on Month 12 post randomization.

At a minimum, all patients who discontinue study drug, including those who refuse to return for a final visit, will be contacted for safety evaluations during the 30 days the last dose of study drug.

Patients who discontinue study drug should be considered withdrawn from the study when it is clear that the patient will not return for the Month 12 assessments.

For patients who are lost to follow-up (i.e. those patients whose status is unclear because they fail to appear for study visits without stating an intention to withdraw), the investigator should show "due diligence" by documenting in the source documents steps taken to contact the patient, e.g. dates of telephone calls, registered letters, etc.

Suspicion of thrombotic microangiopathy is raised when creatinine levels increase more than 50% from previous level in combination with thrombocytopenia and signs of hemolysis. In these cases everolimus should be discontinued and clinical workout is required (e.g. blood smear, kidney biopsy, etc).

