#### Possible Everolimus Drug Interactions

Everolimus is mainly metabolized by CYP3A4 in the liver and to some extent in the intestinal wall and is a substrate for the multi-drug efflux pump, P-glycoprotein. Therefore, absorption and subsequent elimination of systemically absorbed everolimus may be influenced by medicinal products that affect CYP3A4 and/or P-glycoprotein. Concurrent treatment with strong 3A4-inhibitors and inducers is not recommended. See also drugs known to interact with tacrolimus (see Appendix 4). Grapefruit and grapefruit juice have the potential to affect the metabolism of drugs metabolized by CYP450 enzymes. Caution should be used in patients being administered everolimus.

Drugs not allowed	Sirolimus	Patients to be discontinued from everolimus if these immunosuppressive drugs are given
	Terfenadine Astemizole Cisapride	Inhibitors of P-450 (CYP), in particular CYP3A (as everolimus) have the potential to increase the exposure to these drugs, resulting in prolongation of QT intervals on ECGs
	Rifampicin Rifabutin	Strong inducers of P-450 (CYP) have the potential to decrease the exposure of everolimus
	Clarithromycin Telithromycin Ritonavir	Strong inhibitors of P-450 (CYP) have the potential to increase the exposure of everolimus
	Itraconazole** Voriconazole** Fluconazole** Ketoconazole**	Strong inhibitors of P-450 (CYP) have the potential to increase the exposure of everolimus
	Cerivastatin Rosuvastatin	Insufficient data available to make recommendations regarding concomitant use of the newer statins and everolimus
	Lovastatin* Simvastatin*	Confirmed interaction between these drugs and drugs which are CYP3A substrates and/or inhibitors
Drugs strongly discouraged	Quinidine Fluoxetine Paroxetine	Potential interaction of everolimus with CYP 2D6 substrates
Drugs necessitating close monitoring	Digoxin	Potential interaction with everolimus has not been evaluated, patients on digoxin should have periodic measurements of digoxin levels

\*Patients requiring treatment with this class of medication should be monitored closely for signs of rhabdomyolysis, such as, dark-colored urine, fever, muscle cramps, pain, spasm, or stiffness, unusual tiredness or weakness.

\*\*Concomitant administration of everolimus and these drugs necessitates close monitoring of everolimus levels. Fluconazole may pose the smallest risk for drug drug-interaction.

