#### **4- CHOLESTEROL**

Cholesterol > 300 mg/dL or > 8 mmol/L:

Dietary instruction is strongly recommended and statin therapy, e.g. fluvastatin, should be considered.

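### Section 6.6.6 bars only lovastatin and gives simvastatin 5 mg as a reference starting dose, while Appendix 3 does not allow simvastatin with everolimus

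*Protocol*

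**What the plan says.** Protocol Section 6.6.6 tells sites to optimize lipid-lowering treatment before reducing study medication. Statins are given according to local practice, with fluvastatin as the example. One statin is excluded: "The use of lovastatin is prohibited in this study". The starting dose is to be "equivalent to 20 mg pravastatin, 5 mg simvastatin or 20 mg fluvastatin", and it may be raised to bring LDL below 130 mg/dL. The section does not distinguish the arms. Its only cross-reference on lipids is to Appendix 5, for everolimus dose adjustment.

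Appendix 3 (Section 13.3), in the table of possible everolimus interactions, has a category of drugs that are not allowed. The last row of that category, before the strongly discouraged category begins, reads "Lovastatin* Simvastatin". The reason given is "Confirmed interaction between these drugs and drugs which are CYP3A substrates and/or inhibitors". An asterisk on the row leads to a footnote: "Patients requiring treatment with this class of medication should be monitored closely for signs of rhabdomyolysis". The row above it in the same category is "Cerivastatin Rosuvastatin", for which the stated reason is insufficient data.

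Appendix 4, on tacrolimus interactions, names no statin.

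**The concern.** The appendix treats lovastatin and simvastatin identically. Section 6.6.6 bans the first and uses the second as a dosing reference. When one statin is banned by name, the natural reading is that the others are acceptable, and naming a simvastatin dose reinforces that reading.

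The situation is likely to arise. On everolimus, Section 6.6.3 says: "Although hyperlipidemia was common over the full exposure range". Appendix 5 says of cholesterol above 300 mg/dL: "Dietary instruction is strongly recommended and statin therapy, e.g. fluvastatin, should be considered". It gives similar advice for triglycerides above 575 mg/dL. At stake is avoidable exposure to a combination that the protocol itself disallows, with rhabdomyolysis as the hazard its own footnote names.

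There is a smaller consequence for the analysis sets. Use of un-allowed medication is a listed reason for per-protocol exclusion (Protocol Section 10.1, SAP Section 1.2). Whether simvastatin in an everolimus patient counts depends on which part of the protocol is applied.

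**Working it through.** The check is a comparison of text; no power, alpha or sample-size calculation is involved.

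**1. Status of each statin named in the two places**

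| Statin | Section 6.6.6 | Appendix 3, everolimus table |
|---|---|---|
| Lovastatin | Prohibited | Not allowed |
| Simvastatin | Reference starting dose, 5 mg | Not allowed |
| Cerivastatin | Not mentioned | Not allowed |
| Rosuvastatin | Not mentioned | Not allowed |
| Pravastatin | Reference starting dose, 20 mg | Not listed |
| Fluvastatin | Reference starting dose, 20 mg | Not listed |

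Appendix 3 has 4 statins in the not-allowed category and Section 6.6.6 prohibits 1, which leaves 4 − 1 = 3 not carried over. For two of these Section 6.6.6 is merely silent. For simvastatin the two texts contradict each other.

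**2. Does anything direct a site from 6.6.6 to the Appendix 3 restriction?** Section 6.6.6 refers to Appendix 5 for lipids. Appendix 5 recommends considering a statin and lists none as prohibited. The body text points to Appendix 3 in Section 6.6.5, under treatment of oral Candida, and there the subject is azoles. A site managing lipids from 6.6.6 and Appendix 5 would not meet the simvastatin restriction.

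**3. Can an eligible patient already need a statin at randomization?** Randomization exclusion criterion 6 (Section 5.1) removes only uncontrolled cholesterol above 350 mg/dL or triglycerides above 750 mg/dL. The Appendix 5 thresholds for considering a statin are 300 and 575 mg/dL.

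- Cholesterol: eligible and above the threshold from just over 300 to 350 mg/dL, a window of 350 − 300 = 50 mg/dL.
- Triglycerides: eligible and above the threshold from just over 575 to 750 mg/dL, a window of 750 − 575 = 175 mg/dL.

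So a patient can enter Arm I already meeting the threshold. This shows that statin need is foreseeable from the start; it does not show that simvastatin would be chosen.

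**4. Who is affected?** The table concerns everolimus, which is assigned in Arm I only: 165 of 330 planned patients (Section 5), or 165/330 = 50%. That is an upper bound on planned exposure. The number given simvastatin cannot be derived from the documents.

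**The case against.** The strongest counter-argument is that Appendix 3 is not an absolute ban. Only the azole and the lovastatin/simvastatin rows carry asterisks, and both footnotes describe monitoring for patients who do receive the drug. The starred rows could therefore mean: avoid, but monitor if needed. A low simvastatin dose in 6.6.6 would then be compatible with the footnote, and the 5 mg figure may be only a potency yardstick. This does show that Appendix 3 is ambiguous within itself, but it does not resolve the conflict. The footnote attaches equally to lovastatin, which 6.6.6 prohibits outright. The azoles have an exception stated in Section 6.6.5, for systemic infection, and simvastatin has none. Even as a yardstick, the sentence leaves simvastatin usable, because choice follows local practice and only lovastatin is barred.

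There are partial safeguards:

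- Exclusion criterion 7 screens out patients taking significantly interacting drugs, but it acts at entry and does not govern a statin started later.
- CPK is in the blood chemistry panel, but Appendix 2 sets no notable threshold for it.
- Fluvastatin is the named example in 6.6.6 and Appendix 5, which steers sites but does not restrict them.

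Two further points stand. The table was read from PDF, so the extent of the not-allowed category is inferred from row order; that lovastatin shares the row and is prohibited in the body supports the reading for simvastatin. And silence in 6.6.6 on cerivastatin and rosuvastatin is a gap in cross-referencing, weaker than the contradiction over simvastatin.

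**Conclusion.** The concern holds. For patients on everolimus, Section 6.6.6 admits simvastatin and gives a titratable reference dose for it, while Appendix 3 disallows it. A stated rule, followed as written, could lead to a disallowed drug being given, so this is more than a missing detail. It should be corrected on safety grounds.

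Its reach is limited to everolimus patients who are given simvastatin, a number the documents do not supply. The primary analysis on the full analysis set, the sample size and the power are not affected. Per-protocol criteria are set in Module 3 of the VAP documentation, which is not among the documents, so nothing is claimed about how simvastatin was classified there. The conclusion assumes that the not-allowed category runs down to the strongly discouraged label, as the row order indicates.

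**What to change.** - In Section 6.6.6, delete the simvastatin dose from the starting-dose sentence and keep pravastatin 20 mg and fluvastatin 20 mg.
- Keep the lovastatin prohibition, add that simvastatin is prohibited with everolimus, and refer to Appendix 3 so that cerivastatin and rosuvastatin are covered.
- Limit the Appendix 3 rhabdomyolysis footnote to statins that are permitted.
- Apply the same status when un-allowed medication is classified in the VAP deviation list.

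Wording the prohibition as applying with everolimus leaves Arm II free to use simvastatin by local practice at an equivalent dose. The cost is a few words in one section and one footnote. Two reference statins remain available, and the design, sample size and primary analysis do not change.
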